Appendix 3: Measuring the impact of infection on adverse pregnancy, maternal and neonatal outcomes

Noted below are amendments required to the study design to examine the impact of COVID-19 infection (rather than vaccination) on adverse pregnancy, maternal and neonatal outcomes.

Study population	Same study population as for vaccination exposure (described in Section 3.2).
Study period	
This matched cohort study will cover the time period 01 January 2015 to the date of data extraction for the analyses, with the exclusion of the time period when testing for COVID-19 infection was not widespread:
 
 • Pre-pandemic period (01 January 2015 to 29 February 2020) • Pandemic pre-widespread testing period (from 01 March 2020 to 17 May 2020; not included in the analyses on impact of infection on outcomes) • Pandemic widespread testing period (from 18 May 2020 to date of data extraction)
Exposure	
The primary exposure to be investigated in the analyses is any confirmed COVID-19 (indicated by positive PCR test for SARS-CoV-2 virus) from six weeks preconception to the end of an outcome-specific exposure period within pregnancy (Yes/No). The date of onset of COVID-19 is defined as the date the woman's first positive PCR sample was taken. Subsequent positive PCRs within 90 days of an index positive result are discounted. Any positive test taken >90days following the first positive sample is taken as indicating a second infection, and so on.

Outcomes	
The timing of COVID-19 infection for each outcome (ie the outcome specific exposure period) is the same as is included for vaccination (see Table 2).
 
So, for example, for the outcome of miscarriage, we will include women in the COVID-19 infection group if they have a confirmed COVID-19 diagnosis between six weeks preconception and 23⁺⁶ weeks of gestation.

Covariates	Same covariates as for vaccination exposure (described in Section 4).
Matching	
There will be three main analyses for all outcomes, each with a different set of inclusion criteria for the matching process, as follows:
 
Match 1 (primary): Exposed: women who had COVID-19 infection during the pandemic widespread testing period from six weeks preconception or in pregnancy but before the end of the outcome-specific exposure period, excluding any women who received vaccination for COVID-19 from six weeks preconception to the end of the outcome-specific follow-up period. Unexposed group: women from the pre-COVID-19 time period who had been followed-up to the end of the outcome-specific follow-up period by the 29th February 2020, matched to exposed women on maternal age, gestational age and season of conception.
 
Match 2:

	
Exposed: women who had COVID-19 infection during the pandemic widespread testing period from six weeks preconception up to the end of the outcome-specific exposure period, excluding any women who received vaccination for COVID-19 from six weeks preconception up to the end of the outcome-specific follow-up period.
 
Unexposed group: women from the pandemic widespread testing period who did not have confirmed COVID-19 infection from six weeks preconception up to the end of outcome-specific exposure period and did not receive vaccination for COVID-19 from six weeks preconception to the end of the outcome-specific follow-up period, matched to exposed women by maternal age, gestational age, and date of infection.
 
Match 3:
 
Exposed: all women who had COVID-19 infection during the pandemic widespread testing period from six weeks preconception up to the end of the outcome-specific exposure period (i.e. including any women who received vaccination for COVID-19 at any time).
 
Unexposed group: women from the pandemic widespread testing period who did not have confirmed COVID-19 infection from six weeks preconception up to the end of the outcome-specific exposure period (i.e. including any women who received vaccination for COVID-19 at any time), matched to exposed women on maternal age, gestational age, and date of infection.

Analytical approach	Same analytical approach as for vaccination exposure (described in Section 4).

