Outcomes have been aligned as far as possible with the relevant Brighton/GAIA outcome definitions, and also agreed with those in the MHRA / four nations working group on COVID-19 vaccination in pregnancy and comply with those recommended by the WHO³. See Appendix 2 for full rational and sources of information behind included outcomes, definitions, timings etc. as presented in Table 2.

Both primary and secondary outcomes are of interest, with the former being a composite measure including the associated secondary outcomes, and the latter being a narrower measure or subset of the associated primary outcome, e.g. primary outcome = small for gestational age, secondary outcome = very small for gestational age.

Venous thromboembolism in pregnancy is a standard maternal outcome that may be influenced by infection or vaccination and is not the same as vaccine associated thrombosis with thrombocytopenia (VATT), the condition associated with the AstraZeneca vaccine⁴. Similarly, the pregnancy related bleeding outcome includes disseminated intravascular coagulation (DIC) which can occur in association with massive obstetric haemorrhage: again, this is distinct from VATT. Full lists of ICD10 codes used to identify the maternal outcomes venous thromboembolism, pregnancy-related bleeding, and hypertensive disorders of pregnancy are shown in Appendix 1.

³ <https://www.who.int/publications/m/item/safety-surveillance-of-covid-19-vaccines-in-pregnant-and-breastfeeding-women>

⁴ Pavord, S et al (2021). Clinical Features of Vaccine-Induced Immune Thrombocytopenia and Thrombosis. NEJM. DOI: 10.1056/NEJMoa2109908

'Clean windows' will be applied to outcomes, where appropriate, so that only new or incident cases occurring post vaccination will be counted. Specifically, a clean window of the current pregnancy will be applied for the venous thromboembolism, pregnancy-related bleeding, and hypertensive disorders of pregnancy outcomes (i.e. women will only be included if there is no prior record of these outcomes in the current pregnancy). See Table 2. For both congenital anomalies and pregnancy-related bleeding, further descriptive analyses will be conducted looking at more specific diagnoses within these broader outcome groups if we find evidence for an association between vaccination and these outcomes. For example, for pregnancy-related bleeding, we can further disaggregate into early pregnancy bleeding, obstetric haemorrhage, and DIC.

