Longer term child outcomes, including immune function and infection, and neurodevelopment, will be addressed in future work as required.

Other adverse outcomes that are not specific to pregnant women, will be investigated separately for the whole population as part of wider adverse events monitoring in Scotland. If these analyses suggest any signals in the pregnant population, those outcomes would be investigated in the pregnant population using the COPS data infrastructure, as required.

Table 2: Maternal, pregnancy and neonatal outcome measures for monitoring of safety of COVID-19 vaccination in pregnancy

Outcome measure	Definition	Primary or secondary outcome?	Clean window requirement to identify incident cases	Timing of vaccination to be included	Post vaccination risk period to be examined	Estimated background risk of outcome (%)
Maternal outcomes						
Hypertensive disorders of pregnancy	See ICD10 code list. Note that hypertensive disorders can only be diagnosed at >20 weeks.	Primary	No prior record in this pregnancy	Any	Up to E plus PP	10.0
Venous thromboembolism	See ICD10 code list	Primary	No prior record in this pregnancy	Any	Up to E plus PP	0.15
Pregnancy-related bleeding	See ICD10 code list	Primary	No prior record in this pregnancy	Any	Up to E plus PP	30.0 (for postpartum haemorrhage)
ICU admission or death (any cause)	ICU admission as identified on SICSAG record Death from any cause	Primary	None (but exploration to be undertaken of reasons for any pre-vaccination ICU admission where these are documented)	Any	Up to E plus PP	Unknown
Pregnancy outcomes						
Miscarriage	Miscarriage at <24 completed weeks gestation	Primary	None	Up to 23w+6d gestation	Up to 23+6 gestation	10.0 – 20.0

• First trimester miscarriage	Miscarriage at <14 completed weeks gestation	Secondary	None	Up to 13+6 gestation	Up to 13+6 gestation	Unknown
• Second trimester miscarriage	Miscarriage at 14-<24 completed weeks gestation	Secondary	None	Up to 23+6 gestation	14+0 to 23+6 gestation	Unknown
Ectopic pregnancy	Ectopic pregnancy ending at any gestation	Primary	None	Up to 2+6 gestation	Up to E	1.0
Stillbirth	Spontaneous fetal loss at ≥24 completed weeks gestation Any cause of fetal death Losses related to termination of pregnancy excluded	Primary	None	Any	24+0 to E	0.4
Baby outcomes (live births only unless otherwise stated)						

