Any congenital anomaly (relevant pregnancy outcome only)	Any major congenital anomaly as defined by EUROCAT (including live born babies diagnosed at <28 days of age and affected pregnancies resulting in spontaneous loss at ≥20 weeks or termination of pregnancy at any gestation)	Primary	None	Up to 9+6 gestation	At E plus NN	2.7
• Any non-genetic congenital anomaly (relevant pregnancy outcome only)	Any major congenital anomaly as defined by EUROCAT, excluding anomalies with known underlying genetic basis as per standard EUROCAT rules (including live born babies diagnosed at <28 days of age and affected pregnancies resulting in spontaneous loss at ≥20 weeks or termination of pregnancy at any gestation)	Secondary	None	Up to 9+6 gestation	At E plus NN	2.3
Microcephaly	Congenital microcephaly (i.e. present at birth) OFC on delivery record <2SD below	Primary	None	Any	At E	2.0

	mean for sex and gestation at delivery by WHO-UK90 growth reference Babies with anencephaly excluded					
• Severe microcephaly	Congenital microcephaly (i.e. present at birth) OFC on delivery record <3SD below mean for sex and gestation at delivery by WHO-UK90 growth reference Babies with anencephaly excluded	Secondary	None	Any	At E	0.4
Preterm birth	Delivery at <37 completed weeks gestation	Primary	None	Up to 36+6 gestation	Up to 36+6 gestation	7.0
• Very preterm birth	Delivery at <32 completed weeks gestation	Secondary	None	Up to 31+6 gestation	Up to 31+6 gestation	1.0
Spontaneous preterm birth	Delivery at <37 completed weeks gestation following P-PROM or spontaneous onset of labour	Primary	None	Up to 36+6 gestation	Up to 36+6 gestation	4.0
• Spontaneous very preterm birth	Delivery at <32 completed weeks gestation following P-PROM or spontaneous onset of labour	Secondary	None	Up to 31+6 gestation	Up to 31+6 gestation	0.6
Small for gestational age	Birthweight <10th centile by WHO-UK90 growth reference	Primary	None	Any	At E	10.0
• Very small for gestational age	Birthweight <3rd centile by WHO-UK90 growth reference	Secondary	None	Any	At E	3.0
Low Apgar score	5 min Apgar <7	Primary	None	Any	At E	1.5
• Very low APGAR score	5 min Apgar <4	Secondary	None	Any	At E	0.5
Neonatal death	Death from any cause	Primary	None	Any	E plus NN	0.2
Extended perinatal mortality (total births)	Stillbirth or neonatal death from any cause	Primary	None	Any	Up to E plus NN	0.6

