Notes: If timing of vaccination during pregnancy is specified as 'any', this means that women vaccinated at any point from six weeks preconception to date of end of pregnancy (E) will potentially be included in the analysis dependent on the woman being followed-up to the end of the outcome-specific follow-up period. For longer term risk periods: E is date of end of pregnancy; PP is mother's postpartum period, i.e. 6 weeks following delivery (E to E+41); NN is baby's neonatal period, i.e. 4 weeks following live birth (E to E+27). The pregnancy specific maternal outcomes listed above require follow-up to the end of the postpartum period (E+41) for mothers and the end of the postnatal period (E+27) for babies.

3.5.2: Exposure

The primary exposure to be investigated in the analyses is **any** receipt of COVID-19 vaccine from six weeks before conception to the end of an outcome-specific exposure period within pregnancy (Yes/No). The exposure periods for vaccination varies for each outcome (referred to as “outcome-specific exposure period” throughout this protocol), as outlined in Table 2. For ectopic pregnancy, for example, the exposed group will include women who were vaccinated between six weeks before conception up to 2⁺⁶ weeks gestation, while for stillbirth the vaccine exposure period is extended up to the end of the pregnancy.

Subgroup analyses will be conducted where sample size permits, further stratifying women who received their COVID-19 vaccine within the outcome-specific exposure period by: (1) the number of doses received; (2) by the class of vaccine(s) received and; (3) by the type of vaccine(s) received. For the latter two subgroup analyses, we will exclude women who received multiple different classes or types of vaccine within the outcome-specific exposure period. These results will need to be interpreted with caution given that some types of vaccination will be linked to specific sub-groups of women. For example, early in the vaccination programme women who were frontline health or care workers were more likely to receive the Pfizer/BioNTech vaccine, whereas women who were clinically (extremely) vulnerable were more likely to receive the AstraZeneca vaccine. There is therefore potential for residual confounding in comparative analyses examining outcomes following receipt of specific vaccine types.

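### Appendix 3 counts a PCR first positive at the preterm-delivery admission as prior infection, which pushes the null odds ratio for preterm birth above 1

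*Protocol*

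**What the plan says.** Protocol Appendix 3 lists what must change when infection replaces vaccination as the exposure. Exposure is confirmed COVID-19, shown by a "positive PCR test for SARS-CoV-2 virus) from six weeks preconception to the end of an outcome-specific exposure period within pregnancy (Yes/No". On dating, it says "The date of onset of COVID-19 is defined as the date" of the first positive PCR sample. On timing, it says the window ("ie the outcome specific exposure period) is the same as is included for vaccination").

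Those windows are in Table 2 (section 3.5.1):

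- **Preterm birth**, defined as "Delivery at <37 completed weeks gestation": exposure up to 36+6, risk period up to 36+6, clean window none, background risk 7.0%. Very preterm birth is built the same way at 31+6, with 1.0%.
- **Stillbirth, and ICU admission or death**: exposure timing is given as any. By the notes to Table 2, this means women exposed "from six weeks preconception to date of end of pregnancy (E) will potentially be included". Stillbirth has no clean window. For ICU or death the entry is "None (but exploration to be undertaken of reasons for any pre-vaccination ICU admission where these are documented".
- **Clean windows**: section 3.5.1 says "a clean window of the current pregnancy will be applied for the venous thromboembolism, pregnancy-related bleeding, and hypertensive disorders of pregnancy outcomes".

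Match 1 uses pre-pandemic controls matched on maternal age, gestational age and season of conception. Match 2 controls are "matched to exposed women by maternal age, gestational age, and date of infection", and Match 3 uses the same factors. No Match conditions on being admitted or tested. In Matches 2 and 3 a woman with confirmed infection inside the exposure window cannot be a control.

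**The concern.** A vaccination date is seldom set by the onset of labour. A PCR sample can be, if women are swabbed when they come into hospital. A window that is harmless for vaccination can therefore let the outcome create the exposure when it is reused for infection.

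For preterm birth this works in one direction only. A woman first found positive at her preterm-delivery admission enters the exposed group with an outcome risk of essentially 1. Her controls are women pregnant in the same gestational week, most of whom go on to term. Women who deliver at term and are swabbed then fall outside the window, which closed at 36+6, so they do not offset her. In Matches 2 and 3 she also cannot serve as a control. The result is an apparent harm of infection that has nothing to do with infection.

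**Working it through.** The protocol gives no figure for the infection analysis, so there is nothing to reproduce. The check asks how large the null odds ratio (OR) becomes.

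**1. OR for a given share of admission-detected women.** Let p be the outcome risk without any effect (Table 2) and x the share of exposed women first positive at the outcome admission. Their risk is 1, so the exposed risk is x + (1−x)p. Dividing the exposed odds by p/(1−p) gives OR = 1 + x / [(1−x)p].

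Preterm birth, p = 7%:

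- x = 0.5%: exposed risk 7.47%, OR 1.07
- x = 1%: exposed risk 7.93%, OR 1.14
- x = 2%: exposed risk 8.86%, OR 1.29

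Very preterm birth, p = 1%:

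- x = 0.5%: OR 1.50
- x = 1%: OR 2.01

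**2. What x might be.** This needs assumptions, because the documents give neither admission-testing practice nor detection rates. Suppose infection is independent of outcome, a share a of infections is detected before any admission, undetected infections stay PCR-positive for D weeks, and every woman delivering preterm is tested. The exposure window runs from gestational week −4 to week 36, about W = 41 weeks. Weekly incidence cancels, and roughly x/(1−x) = (1−a)Dp/(aW), so OR ≈ 1 + (1−a)D/(aW).

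- a = 0.5, D = 1: 1 + 0.5/20.5 = 1.02
- a = 0.5, D = 3: 1 + 1.5/20.5 = 1.07
- a = 0.2, D = 2: 1 + 1.6/8.2 = 1.20

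A fuller calculation, week by week, with D from 1 to 3, gives null ORs for preterm birth of:

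- a = 0.7: 1.01 to 1.03
- a = 0.5: 1.03 to 1.08
- a = 0.3: 1.06 to 1.19
- a = 0.2: 1.11 to 1.32
- a = 0.1: 1.24 to 1.73

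Across these, x runs from 0.07% to 4.4%. When samples first taken at the outcome admission are not counted, the OR is 1.00 in every scenario.

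**3. Chance of a false signal.** Assume 5,000 exposed and 15,000 controls. These are the vaccination figures of section 3.7; none is given for infection. With D = 2, two-sided 0.05 and no multiplicity correction, the chance of a significant result under the null is about 13% at a = 0.5, 46% at a = 0.3 and 87% at a = 0.2.

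**4. Outcomes with exposure to the end of pregnancy.** Here testing at ordinary deliveries adds exposed women without the outcome, which dilutes the effect.

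- **ICU or death**: with an assumed risk of 0.1% or 0.5%, 25% or 50% of it antenatal, all women tested at delivery, D = 2 and a from 0.1 to 0.5, the null relative risk is about 1.01 to 1.21.
- **Stillbirth**: with assumed gestation-specific risks, the null OR is about 1.02 to 1.23.
- **Bleeding**: modelled the same way, the null OR is 1.00 to at most 1.01.

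**The case against.** The strongest objections concern scope, size and remedy.

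- **Bleeding.** A reader might infer that every outcome that brings a woman into hospital is affected. The clean window contradicts this for bleeding, venous thromboembolism and hypertensive disorders: a woman whose event is recorded before her positive sample is excluded, and only same-day ordering stays open. The background risk listed for bleeding is for postpartum haemorrhage, which follows an admission swab. This objection stands.
- **Admission testing.** No passage says women are swabbed on admission. Appendix 2 cites a study of confirmed COVID-19 at delivery, but as a source for choosing outcomes, not as a statement of Scottish testing practice. The size is therefore conditional. The appendix also leaves out the period before widespread testing, which makes very low community detection less likely.
- **Controls.** They are not required to be unadmitted. They are women at the same gestation, mostly not being admitted.
- **Existing check.** Section 4.3 plans plots of time from index to outcome, and Appendix 3 inherits Section 4. A cluster at day zero might show there. It would correct no estimate.
- **Redefining exposure.** Requiring every positive sample to precede the admission looks tidy. For ICU or death it would delete women admitted because of COVID-19, which is the effect under study, and so bias toward no effect. This stands, and it rules out redefinition as the remedy.
- **Left to the analysis plan.** A sensitivity analysis could sit in a plan not shown here. But the exposure rule is fully stated in Appendix 3, and following it as written produces the bias for preterm birth.

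**Conclusion.** The point holds for preterm and very preterm birth. Exposure and risk periods end together, there is no clean window, and nothing requires the positive sample to precede the outcome admission, so any first detection at that admission moves the null OR upward.

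The size is assumption-dependent. It is about 1.07, 1.14 or 1.29 for preterm birth if 0.5%, 1% or 2% of exposed women are first detected at the outcome admission. It is about 1.03 to 1.08 if half of infections are found earlier, and larger if community detection is low. A reader might take the upper values (1.7 or so) as typical, but they need only a tenth of infections to be found beforehand, and the documents do not support that as the expected case.

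For stillbirth and for ICU admission or death the same direction is plausible, less certain and probably smaller. Bleeding, venous thromboembolism and hypertensive disorders are largely protected. The point concerns the infection extension only and does not touch the vaccination comparison that is the protocol's main aim.

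**What to change.** Keep the main exposure definition in Appendix 3. Add a pre-specified sensitivity analysis for each of Matches 1, 2 and 3, covering preterm birth (with its very preterm form), stillbirth, and ICU admission or death. It should exclude exposed women whose first positive sample was taken on or after the date of the admission at which the outcome occurred, together with their matched controls. Report how many women are excluded for each outcome, since that count gives x directly.

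For ICU or death, state in advance that the result is read as a bound, because some of those positives reflect a true effect of infection.

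The dates needed (PCR sample and hospital or critical-care admission) come from sources the protocol already links. The cost is one extra run per Match and slightly fewer exposed women in that analysis.

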With the pre-pandemic period being used as the baseline, there is an assumption that the pandemic has not substantially affected the outcomes of interest through, for example, changes in engagement and provision of maternity services. To investigate this, a supplementary analysis will be conducted with pregnant unvaccinated controls from the pandemic vaccination period (from 08 December 2020 to date of data extraction). In this supplementary analysis, we will exclude women (from both the vaccinated and unvaccinated group) who had any record of COVID-19 infection from six weeks preconception to the end of the outcome-specific follow-up period. However, given that there is potential for vaccination to impact on maternal, pregnancy and neonatal outcomes by changing the risks of acquiring COVID-19 and experiencing severe illness, we will also conduct a second supplementary analysis with pregnant unvaccinated controls from the pandemic. In this, we will retain both vaccinated and unvaccinated women with a confirmed record of COVID-19 infection during pregnancy and preceding the end of the outcome-specific follow-up period. For both these supplementary analyses, women who were vaccinated >6 weeks pre-conception will be included in the control group (as not vaccinated in pregnancy), however sensitivity analyses (if sample size permits) will be conducted to investigate any differences between pairs where the control is completely unvaccinated versus pairs where the control received vaccination >6 weeks pre-conception (e.g. vaccinated pre-‘pregnancy’). Additional supplementary analyses removing women who are vaccinated in the six weeks preconception will be considered for the analyses using women from the pandemic period as controls, if we observe an impact of removing these women in the primary analysis using pre-pandemic controls.

Maternal and gestational age are known to be important risk factors for adverse events in pregnancy (e.g. miscarriage strongly influenced by maternal age). Consequently, the cohorts will be matched by maternal age (± 1 years but relaxed (i.e. possibly $\pm >1$ year) at the tails of maternal age distribution as fewer individuals available for matching), and gestational age (exact match, i.e. same week however allow for relaxation of this at the tails of the gestation distribution).

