First, a model with no covariates will be fitted to calculate the unadjusted OR for the association between vaccination status and each outcomes of interest. Subsequently, we will calculate an adjusted OR for the association between vaccination status and each outcomes of interest, by adding all covariates to the model (Table 4). P-values and confidence intervals will be reported for all models. For some rarer outcomes, we will adjust our modelling approach as required (e.g. re-classification of groupings or removing insignificant covariates). Covariate pairs will be assessed for collinearity before adding to the model. For any covariate pairs that are highly correlated, only the covariate which has the biggest impact on the association between the exposure and outcome will be included in the model.

As previously described (section 3.5.2), analyses will be conducted first looking at the association between having any vaccination and outcomes, and then in sub-group analyses stratified by vaccine classes and individual vaccine types;

- Vaccine type: Pfizer, AstraZeneca, Moderna, Janssen
- Vaccine group: Pfizer and Moderna (mRNA); AstraZeneca and Janssen ((adeno)virus vector)
- Number of vaccine doses

Our main analyses will include all pregnancies/births, regardless of whether there is evidence that it was singleton or multiple, with sensitivity analyses conducted restricting to only pregnancies/births where there was no evidence it was a multiple. We often do not know whether pregnancies which end early (e.g. due to miscarriage) were singleton or multiple, hence the decision to only include pregnancies with *no evidence* of being a multiple in these sensitivity analyses.

4.5: Additional analyses

There are two further analyses that may subsequently be conducted to assess the association between vaccination and adverse outcomes, specifically:

1. We will consider using all data from the pre-pandemic period to predict the expected number of outcomes among the vaccinated pregnant women, and compare this predicted number to the observed number within the vaccinated group of women.
2. For rarer outcomes (e.g. for congenital anomalies, microcephaly), we will consider a nested case control study if signals are identified in this present matched cohort analysis but wide confidence intervals due to the small number of events negate any meaningful conclusions. This design maximises power to assess any association between vaccination and these rare outcomes.

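### Appendix 3, Match 3 keeps vaccinated women in both groups but neither matches on nor adjusts for doses received before the infection date, leaving its odds ratio open to avoidable confounding

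*Protocol*

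**What the plan says.** Appendix 3 sets out what changes when the exposure becomes COVID-19 infection instead of vaccination. On matching it states: "There will be three main analyses for all outcomes, each with a different set of inclusion criteria for the matching process". Match 1 is labelled primary.

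- **Match 3, exposed:** "all women who had COVID-19 infection during the pandemic widespread testing period", with women vaccinated at any time explicitly included.
- **Match 3, unexposed:** uninfected women from the same period, "including any women who received vaccination for COVID-19 at any time), matched to exposed women on maternal age, gestational age, and date of infection". No other matching factor is given.
- **Match 2, unexposed, for contrast:** women who "did not receive vaccination for COVID-19 from six weeks preconception to the end of the outcome-specific follow-up period". The exposed groups of Matches 1 and 2 carry the same exclusion.
- **Covariates:** "Same covariates as for vaccination exposure (described in Section 4". The list itself is in Table 4 of Section 3.5.3.
- **Analysis:** "Same analytical approach as for vaccination exposure (described in Section 4". Section 4.4 obtains the adjusted odds ratio "by adding all covariates to the model (Table 4".

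Table 4 lists deprivation, urban-rural status, ethnicity, pre-pregnancy clinical vulnerability, diabetes, BMI and smoking. It has no entry for vaccination status or number of doses.

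**The concern.** Leaving vaccination out of Table 4 is right when vaccination is the exposure. Once infection is the exposure, a dose given before the infection date comes before the exposure and is a candidate confounder. Appendix 3 changes the exposure but leaves the covariate list as it was.

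The protocol supplies both links that confounding needs, as possibilities:

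- **Vaccination and infection.** Section 3.6 says that "there is potential for vaccination to impact on maternal, pregnancy and neonatal outcomes by changing the risks of acquiring COVID-19 and experiencing severe illness".
- **Vaccination and outcome by another route.** Section 5.0, item 6, acknowledges that vaccinated and unvaccinated women may differ in unmeasured ways, such as occupation and engagement with antenatal care. Objective 2 in Section 2.0 asks whether these same outcomes differ by vaccination, so the infection analysis cannot take it for granted that they do not.

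At stake is one of the three main infection analyses, and the only one that covers women vaccinated between six weeks preconception and the end of follow-up. Any contrast between Match 2 and Match 3 would also be harder to interpret, because part of the difference could reflect who had been vaccinated.

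**Working it through.** **Does the design balance prior doses anywhere?**

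1. *Matching.* Maternal age and gestational age do not determine vaccination. Matching on the infection date balances calendar time and vaccine availability. It does not balance which women had been dosed by that date.
2. *Adjustment.* Table 4 has no vaccination term. Variables such as deprivation, ethnicity and clinical vulnerability may remove part of the difference between vaccinated and unvaccinated women, but not a direct link between vaccination and infection.
3. *Subgroups.* The dose, class and type subgroups in Section 4.4 divide vaccination as an exposure. They are not stated as an adjustment for Match 3.
4. *Calendar limits.* The testing period opens on 18 May 2020 (Appendix 3) and the vaccination period on 08 December 2020 (Section 3.3). Women in sets indexed before 08 December 2020 have no prior doses to balance.

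**How large could the bias be?** The protocol states no figure for this point, so there is none to reproduce. The inputs below are assumptions; the documents give no uptake by infection status and no association between vaccination and outcome.

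- v0: share of uninfected women dosed before the index date
- v1: share of infected women dosed before the index date
- OR: odds ratio linking prior vaccination to infection
- r: outcome risk ratio, vaccinated to unvaccinated, by routes other than infection

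Where v1 is not set directly, odds1 = OR × v0/(1 − v0) and v1 = odds1/(1 + odds1). With no true infection effect,

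spurious RR = (1 − v1 + v1·r) / (1 − v0 + v0·r).

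Worked case: v0 = 0.60, OR = 0.3, r = 0.7. Then odds1 = 0.3 × 1.5 = 0.45 and v1 = 0.45/1.45 = 0.310. The numerator is 1 − 0.310 × 0.3 = 0.907, the denominator is 1 − 0.60 × 0.3 = 0.82, and the ratio is 1.11.

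| v0 | OR | v1 | r | spurious RR |
|---|---|---|---|---|
| 0.10 | 0.3 | 0.032 | 0.7 | 1.02 |
| 0.10 | 0.3 | 0.032 | 1.2 | 0.99 |
| 0.30 | 0.5 | 0.176 | 0.8 | 1.03 |
| 0.60 | 0.3 | 0.310 | 0.7 | 1.11 |
| 0.60 | 0.3 | 0.310 | 1.2 | 0.95 |
| 0.50 | – | 0.30 (set) | 0.8 | 0.94/0.90 = 1.04 |
| 0.60 | – | 0.20 (set) | 0.7 | 0.94/0.82 = 1.15 |

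Over v0 from 0.1 to 0.6, OR from 0.3 to 1.0 and r from 0.7 to 1.2, the range is 0.95 to 1.11. The last row lies outside that grid: 20% against 60% implies an odds ratio of (0.2/0.8)/(0.6/0.4) = 0.17. The bias is exactly zero if OR = 1 or r = 1. Within strata of prior doses v1 = v0, so the spurious RR from measured vaccination status becomes 1.00.

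The figures are risk ratios for sets in which prior vaccination was possible, with no credit for Table 4 adjustment. Sets from before 08 December 2020 would dilute them.

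**The case against.** The case on the other side has several parts.

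**Confounding is possible, not demonstrated.** This stands. The routes named in Section 3.6 both run through infection: acquiring it, and how severe it is. The severity route is effect modification, not confounding. A link from vaccination to outcome outside infection rests on Section 5.0, which speaks only of potential, and on the open question in Objective 2. A reader might infer that Match 3 is confounded as a matter of fact; the documents support only that it may be.

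**The direction is unknown.** This also stands. A reader might expect fewer previously dosed women among the infected. The documents give no such figure, and Section 3.5.2 notes that vaccine types were tied to particular groups, such as frontline health or care workers, whose exposure to infection may also have differed.

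**Match 3 is not the only analysis that can contain vaccinated women.** Correct. Matches 1 and 2 exclude vaccination only from six weeks preconception onward. Women vaccinated earlier can remain in both groups of Match 2 and in the exposed group of Match 1. It follows that Match 2 is not a fully clean comparator and needs the same covariate.

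**Safeguards exist.** Match 1 is primary, date matching helps, Table 4 helps in part, and Section 5.0 discloses unmeasured confounding. These limit the consequences. They do not remove the gap: prior vaccination is measured, so a caveat about unmeasured factors does not cover it, and neither Match 1 nor Match 2 can stand in for Match 3 for women vaccinated from six weeks preconception onward.

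**Conclusion.** The point holds as a correctable gap in a main but non-primary analysis. Match 3 includes women vaccinated at any time in both groups and makes no provision for doses received before the index date. On the protocol's own premises its odds ratio is open to confounding that measured data could reduce.

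The likely size is modest: a spurious risk ratio of about 0.95 to 1.11, up to 1.15 in an extreme scenario, and none for index dates before 08 December 2020. These values rest entirely on assumed uptake and associations, and the bias vanishes if prior vaccination is unrelated to infection or, apart from infection, to the outcome. A reader might go further and conclude that the Match 3 result cannot be read as an infection effect at all. Biases of this size, in an unknown direction, do not support that.

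**What to change.** In Appendix 3, amend the covariate and matching entries for Match 3 to add the number of vaccine doses received before the infection date, or before the matched index date for uninfected women (0, 1, 2 or 3). Use it either as a covariate in the adjusted model or as a matching variable. Count only doses before that date: later doses follow the exposure, so a classification of vaccinated at any time would not serve.

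Use the same covariate in Match 2, where women vaccinated more than six weeks before conception can remain in both groups. It cannot balance Match 1, because no pre-pandemic control can have had a dose.

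The cost is small. Table 3 already lists the dose dates, so one derived covariate is enough. If it is used for matching, some sets will have fewer controls.
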